8.4.2.1.2 Analysis of Solicited Local, Systemic and Other Adverse Events

Frequencies and percentages of subjects experiencing each AE occurring after first study vaccination, will be presented for each symptom overall and by maximum severity. Summary tables showing the occurrence of any local or systemic AE overall and at each time point will also be presented.

Post-vaccination solicited AEs reported from Day 1 to Day 7 will be summarized for the intervals Day 1-3, Day 4-7, Day 1-7 by maximal severity and by vaccine group, excluding the 30 minute measurement, which will be summarized separately.

The severity of solicited local AEs including injection-site erythema, injection-site induration, injection-site ecchymosis, and either injection-site tenderness (for children

ages 6 months through <3 year) or injection-site pain (for children 3 years and older). Injection-site erythema, induration and ecchymosis will be summarized according to categories: 1 to 10 mm, 11 to 25 mm, 26 to 50 mm, >50 mm. Injection site pain/tenderness and systemic AEs (except fever) occurring up to 7 days after each vaccination will be summarized according to “mild”, “moderate” or “severe”.

Body temperature will be summarized by 0.5 °C and 1.0 °C increments from 36.0°C up to $\geq 40^{\circ}\text{C}$ and will be broken down according by route of measurement. Fever, ie, body temperature $\geq 38^{\circ}\text{C}$ will also be categorized as mild (38.0-38.4°C), moderate (38.5-38.9°C), severe (39.0-40.0°C), and potentially life threatening ($\geq 40.0^{\circ}\text{C}$).

Each solicited local and systemic AE will also be further summarized as “none” versus “any”.

Implausible measurements (for further definition see the SAP) will be left out of the analysis.

Use of antipyretics and analgesics will be summarized by frequency: by type of use (prophylactic versus treatment) and percentage of subjects reporting use.

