1. BACKGROUND AND RATIONALE

Pandemic influenza differs from seasonal influenza by representing a novel influenza strain, to which humans are immunologically naive, and has the potential for heavily impacting a young otherwise healthy population. If sustained human-to-human transmission were to occur with a pandemic influenza strain, global spread is likely, and morbidity and mortality could be staggering if efforts to contain the spread were not implemented quickly. Vaccination is the best option by which spread of a pandemic virus could be minimized or prevented. Vaccination efforts would be further enhanced by identification of the fewest number of vaccinations and lowest antigen dose needed for protection of segments of the population.

The present study is a post authorization commitment in Europe. The purpose of this study is to provide additional clinical data on aH5N1 in children in anticipation of an avian influenza pandemic, as agreed in the pediatric investigational plan with EMA/Pediatric Committee. This is a pediatric dose-ranging study for aH5N1 to dosages with decreased content of HA antigen and/or MF59 adjuvant (versus the licensed dosage for adults). The study is designed to evaluate the safety and immunogenicity of two vaccinations using three different amounts of aH5N1 and two different dosages of MF59 adjuvant, administered 3 weeks apart.

For further details please refer to section 1.0 of the protocol.

This plan describes all details related to the statistical analysis of the data collected in the study V87_30 and is based on protocol version 5, 24 JUN 20.

This analysis plan is compliant with ICH Harmonized Tripartite Guideline, 5 February 1998, Statistical Principles for Clinical Trials, E9; World Health Organization, WHO Technical Report, Series No. 924. 2004, Annex 1: Guidelines on Clinical Evaluation of Vaccines: Regulatory Expectations; and FDA Center for Biologics Evaluation and Research (CBER) Guidance for Industry, May 2007, Clinical Data Needed to Support the Licensure of Seasonal Inactivated Influenza Vaccines.

Statistical Analysis Plan, Protocol Number V87_30

06 MAY 2022 Final Version 1.0

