| | | Arthralgia | No interference with daily activity | Interferes with daily activity | Prevents daily activity |
| | | Headache | No interference with daily activity | Interferes with daily activity | Prevents daily activity |
| | | Malaise | No interference with daily activity | Interferes with daily activity | Prevents daily activity |
| Overall | | Shivering/Chills | No interference with daily activity | Interferes with daily activity | Prevents daily activity |
| Overall | | Fever | 38.0 - 38.9 °C | 39 – 39.9 °C | ≥40.0 °C |

Note: presence of an event on a day is defined as mild, moderate or severe; absence is defined as none. Ecchymosis, Erythema and Induration: grading will be derived from the actual measurements in mm; Fever will be derived from the actual measured body temperature.

Statistical Analysis Plan, Protocol Number V87_30

06 MAY 2022 Final Version 1.0

Other Indicators of Reactogenicity

The use of analgesics/antipyretics will be captured as “absent” or “present” separately by reason “for treatment” or “for prevention”.

The analyses will encompass various summaries of the data by vaccination and – where applicable - combined across the two vaccinations using the solicited safety set:

1. Overall summary of subjects with solicited AEs
2. Solicited local AEs, maximum event severity by event and interval
3. Solicited systemic AEs, maximum event severity by event and interval
4. Number of days of solicited AEs, including ongoing AE after Day 7
5. Daily reports of subjects with solicited AEs, only per vaccination
6. Day of first onset of solicited AEs, only per vaccination
7. Solicited AEs ongoing at Day 7
8. Distribution of maximum temperature
9. Other use of analgesics/antipyretics

For each of the time points or time intervals presented in the summaries, only subjects with at least one valid observation (i.e., any non-missing values but excluding “Not done/unknown” and implausible values) for the solicited adverse events in the interval of interest will be considered. Subjects without valid data will be removed from the denominator to prevent a downward bias (towards zero).

All tables are run by age stratum and vaccine group. The local solicited AEs and the common systemic solicited AEs (as defined in Table 3) are also presented combining the two age strata.

Overall summary of subjects with solicited adverse events.

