The **time of first onset** is defined, for each subject, for each solicited AE, as the time point at which the respective solicited AE first occurred. The summary will provide the frequencies and percentages of subjects with first onset of each solicited AEs by vaccine group and by each time point.

For each vaccination the first onset of the AE will be used for each subject.

Statistical Analysis Plan, Protocol Number V87_30

06 MAY 2022 Final Version 1.0

For any vaccination the worst AE across all vaccinations per time point will be used. Note, ‘not done’ is treated identical to ‘missing’.

Solicited adverse events ongoing at Day 7

For each of the solicited AEs, the number of subjects reported the event ongoing at Day 7 will be summarized.

Distribution of maximum temperature

Body temperature will be summarized by 0.5 °C increments from 36.0 °C up to ≥ 40 °C by frequency tables.

Other use of analgesics/antipyretics

The use of antipyretics and analgesics will be summarized by type of use (prophylactic versus treatment) as the number and percentage of subjects reporting use.

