16. CHANGES TO PLANNED ANALYSIS

Not applicable.

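### SAP Table 3 grades fever on a different scale from protocol 8.4.2.1.2 and declares no change, so the threshold for severe-or-worse fever rises from 39.0 to 40.0 °C in the severity tables.

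*SAP*

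**What the plan says.** Protocol 8.4.2.1.2 is the only place in the protocol that gives numeric fever grades. It sets "mild (38.0-38.4°C), moderate (38.5-38.9°C), severe (39.0-40.0°C), and potentially life threatening", with the last category starting at 40.0 °C. Section 7.1.3 refers the reader to 7.1.1 for the grading of solicited events, but 7.1.1 contains no fever grades. Protocol 8.4.2.1.2 also asks for body temperature in both 0.5 °C and 1.0 °C steps, and says that it "will be broken down according by route of measurement".

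SAP 13.2, Table 3, has three grades (mild, moderate, severe), and the fever row reads "Fever | 38.0 - 38.9 °C | 39 – 39.9 °C | ≥40.0 °C". The note under the table says "Fever will be derived from the actual measured body temperature". The SAP then plans maximum-severity tables by event and interval, and a condensed table limited to any and severe events. For temperature itself: "Body temperature will be summarized by 0.5 °C increments from 36.0 °C up to ≥ 40 °C by frequency tables". Route of measurement is not mentioned.

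The SAP says that it "is based on protocol version 5, 24 JUN 20". Its section headed "16. CHANGES TO PLANNED ANALYSIS" reads "Not applicable".

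**The concern.** The study compares six antigen and MF59 contents in children from 6 months of age, and fever is a solicited systemic event in both age cohorts. The protocol fixed its fever bands in advance. In the same section it leaves the definition of implausible readings to the SAP, but it makes no such deferral for the fever cut-offs. The SAP replaces them with milder labels and does not say so.

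Two things are at stake. First, a count headed severe fever in the report will not mean what the protocol said it would, and nothing tells the reader. Second, the condensed table of any and severe events will show fevers of 39.0-39.9 °C only under any. A difference between formulations in that range could not appear there as a difference in severe fever. The effect on severe-or-worse counts runs one way: they can stay the same or fall, but cannot rise.

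**Working it through.** No sample size, power or error rate is involved, so there is no stated figure to reproduce. The check grades every temperature under both scales.

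**Inputs.** Protocol bands from 8.4.2.1.2; SAP grades from Table 3; upper limit of 41.9 °C, because SAP Table 2 removes readings of 42 °C or more. Readings are assumed to be recorded to 0.1 °C.

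**Step 1. Grade 38.0 to 41.9 °C in 0.1 °C steps (40 values).**

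| Maximum temperature (°C) | Values | Protocol | SAP Table 3 | Result |
|---|---|---|---|---|
| 38.0-38.4 | 5 | mild | mild | same |
| 38.5-38.9 | 5 | moderate | mild | lower label |
| 39.0-39.9 | 10 | severe | moderate | lower label |
| 40.0 | 1 | severe and potentially life threatening | severe | depends on how the protocol overlap is settled |
| 40.1-41.9 | 19 | potentially life threatening | severe | lower label |

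Of the 40 values, 5 + 10 + 19 = 34 get a lower label, 5 are unchanged and 1 is ambiguous. The ambiguity is the protocol's own, because its severe band ends at 40.0 °C and its top band begins there.

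**Step 2. Severe or worse.** Under the protocol this is T ≥ 39.0 °C; under the SAP it is T ≥ 40.0 °C. So

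N(SAP, severe) = N(protocol, severe or worse) − N(39.0-39.9 °C).

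The SAP count can never exceed the protocol count. This ordering holds for severe or worse only. The bands labelled severe (39.0-40.0 °C in the protocol, 40.0 °C and above in the SAP) share only the value 40.0 °C, so neither count bounds the other.

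**Step 3. Any fever.** Both scales start at 38.0 °C, so any-fever counts are identical.

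**Step 4. Recovery from the 0.5 °C table.** The protocol cut-offs 38.0, 38.5, 39.0 and 40.0 are all multiples of 0.5, so each falls on a bin edge. If each bin includes its lower edge, as the last bin does:

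- 38.0-38.4 gives mild
- 38.5-38.9 gives moderate
- 39.0-39.4 plus 39.5-39.9 gives severe
- 40.0 and above gives the top band

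This works if exactly 40.0 °C is assigned to the top band. If it were assigned to severe, the last bin could not be split. SAP 13.2 runs its tables by age stratum and vaccine group, but the temperature item names no Day 1-3 or Day 4-7 intervals, unlike the severity tables.

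**Step 5. Scale of the relabelling.** With about 70 children per arm, a proportion p peaking at 39.0-39.9 °C after a dose means 70 × p children move from severe to moderate. The documents give no value for p. Purely as an assumed range, p = 2% gives 70 × 0.02 = 1.4 children and p = 8% gives 70 × 0.08 = 5.6. Per age cohort within an arm (about 35), the figures are 35 × 0.02 = 0.7 and 35 × 0.08 = 2.8. Steps 1 to 4 do not depend on this range.

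**Step 6. Route.** Protocol 7.1.1 prefers oral readings and has any other route recorded on the diary card, so the data for a breakdown exist. SAP 13.2 does not specify one.

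**The case against.** The strongest reply is that little of substance is lost. It disposes of several stronger readings that a reader might infer.

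- **That the primary endpoint changes.** It does not. Protocol 8.1.1.1 defines the endpoint as the share of children with solicited events over four intervals, without grade. Severity enters through the analysis section.
- **That the top category is lost.** The SAP's highest grade is 40.0 °C and above, the same set as the protocol's top category. Those children are still counted separately; only the name changes.
- **That a gradient at 39.0-39.9 °C is hidden.** It is missing from the severe column of the condensed table only. It would show as moderate in the full maximum-severity table and in the 0.5 °C table. The condensed table is described under local events and reaches fever only because systemic events follow the same methods.
- **That a decision depends on the grade.** The study has no hypotheses, success criteria, predetermined stopping rules or data monitoring committee. The text in protocol 3.8 on subsequent vaccination cites a temperature, not a fever grade.
- **That the protocol scale is shown to be the right one.** The documents do not say which scale was intended, and the protocol's own bands overlap at 40.0 °C.
- **That the route breakdown was deliberately removed.** The SAP is silent, and its section 17 leaves the tables to be defined later with their shells.

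All of this stands, and it limits the seriousness. It does not remove the point. A prespecified grading was replaced without notice, and readers can undo the relabelling only if they know it happened and accept a table with no stated time intervals.

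**Conclusion.** The two documents contradict each other on fever severity, and the SAP does not declare the difference. Following the SAP raises the severe-or-worse threshold by 1.0 °C, from 39.0 to 40.0 °C, and relabels every fever from 38.5 °C upward except possibly exactly 40.0 °C. The consequence is confined to reported severity labels. The measured temperatures, any-fever rates and primary endpoint percentages are unaffected, and the protocol bands can be rebuilt for the whole post-dose period. It is a should-fix, not a reason to doubt the data.

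The relabelling follows from the text alone. How many children it touches is unknown, since the documents give no fever incidence. The finding also assumes that the supplied protocol is the version the SAP follows, which cannot be confirmed here because the protocol's title page is not available. The missing route breakdown is a secondary omission and does not raise the severity.

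**What to change.** Reconcile the two scales before unblinding, in one of two ways:

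1. Derive the fever grade in SAP Table 3 by the protocol's bands, including the separate top category, and assign exactly 40.0 °C to one category only.
2. Keep the SAP scale, declare and justify it in SAP 16, and also tabulate fever by the protocol's bands (with 40.0 °C settled) by vaccine group, age cohort and interval.

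Under either option, state the cut-offs in a footnote to every table that reports severe fever. As a secondary change, add to SAP 13.2 the temperature summary by recorded route that the protocol asks for.

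The cost is one derived variable and SAP wording. Temperatures and non-oral routes are already collected, so no new data are needed. Severe-fever rates reported on the protocol's bands may look less favourable.

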The parent(s)/LAR(s) should be advised to begin measuring the subject’s temperature approximately 6 hours after the vaccination or prior to the subject going to bed if this is before. For the next 6 days following vaccination, the subject’s temperature should be measured at least once a day, preferably in the evening and at the same time each day. If the subject feels warm or unusually cold at any time during the 7 day post vaccination reporting period, the parent(s)/LAR(s) should be advised to record an additional temperature. If multiple temperatures are collected on any given day, only the highest temperature measured that day should be recorded.

If the subject’s temperature is below 35.5°C the parent(s)/LAR(s) should be advised to take a repeat measurement to ensure the temperature is correct. If the subject’s temperature is 38.0°C or higher at day 7, the parent(s)/LAR(s) should continue to measure the subject’s temperature each day until it returns below 38.0°C . The date of the last day that the subject’s temperature was above 38.0°C should be recorded on the Subject Diary Card.

If the subject’s temperature is $\geq 38.0^{\circ}\text{C}$ and is accompanied by one or more of the following symptoms: cough, sore throat, nasal congestion or runny nose, the parent(s)/LAR(s) should be advised to contact the study site immediately.

Instructions for Recording Injection Site Reactions

It is important to advise the parent(s)/LAR(s) that they should record both when an injection site reaction was observed as well as when one was not by checking the

appropriate tick box on the Subject Diary Card. The parent(s)/LAR(s) should be advised to complete their assessments at approximately the same time each day, preferably in the evening.

When a measurable reaction is observed such as hardness, bruising or redness the parent(s)/LAR(s) making the assessment should use the ruler provided by the site to measure the size in mm of the affected area. This information should be recorded by the parent(s)/LAR(s) on the Subject Diary Card.

When tenderness at the reaction site is noticed the parent(s)/LAR(s) should monitor the monitor the symptoms throughout the day and enter the most severe status that was observed (ie, mild, moderate or severe). If a reaction continues past day 7 the subject's parent(s)/LAR(s) should be advised to record the last day that the reaction was observed.

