8.1 Endpoints

8.1.1 Primary Endpoint(s)

8.1.1.1 Primary Safety Endpoint(s)

The measures for assessing safety and reactogenicity are as follows:

- Percentages of subjects with solicited local and systemic AEs¹⁰ that occur within 7 days following each vaccination and calculated for 4 time intervals after vaccination: 30 minutes, 1 through 3 days, 4 through 7 days, and 1 through 7 days.
- Percentages of subjects with any unsolicited AEs reported within 21 days after each vaccination within each vaccine group.
- Percentages of subjects reporting SAEs, NOCDs, AESIs, and AEs leading to vaccine and/or study withdrawal, as collected from Day 1 through Day 387.

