13.2 Solicited Local and Systemic Adverse Events

Different diary cards have been used for subjects <3 years and subjects >=3 years.

Each solicited AE is to be assessed for 7 days following each vaccination according to a defined severity grading scale; see specifics of the solicited event and grading system below in Table 3.

Table 3 Severity Grading for Solicited Local and Systemic Adverse Events

| Age group | Type | Solicited Event | Any Event | | |
|------------|-----------------|-----------------------------------|--|---|---|
| | | | Grade 1/Mild | Grade 2/Moderate | Grade 3/Severe |
| Overall | Local | Injection site tenderness or pain | No interference with daily activity | Interferes with daily activity | Prevents daily activity |
| | | Ecchymosis | 11-25 mm | 26-50 mm | >50 mm |
| | | Erythema | 11-25 mm | 26-50 mm | >50 mm |
| | | Induration | 11-25 mm | 26-50 mm | >50 mm |
| < 3 years | Systemic | Change of eating habits | Eating less than normal for 1 - 2 feeds / meals | Missed 1 or 2 feeds / meals | Missed more than 2 feeds /meals |
| >= 3 years | | Loss of appetite | Eating less than usual with no effect on normal activity | Eating less than usual /interfered with normal activity | Not eating at all |
| Overall | | Vomiting | 1 - 2 times in 24 hours | 3 - 5 times in 24 hours | 6 or more times in 24 hours or requires intravenous hydration |

Statistical Analysis Plan, Protocol Number V87_30

06 MAY 2022 Final Version 1.0

| Age group | Type | Solicited Event | Any Event | | |
|------------------|-------------|------------------------|---|--------------------------------|--|
| | | | Grade 1/Mild | Grade 2/Moderate | Grade 3/Severe |
| Overall | | Diarrhea | 2-3 loose stools in 24 hours | 4-5 loose stools in 24 hours | 6 or more loose stools in 24 hours or requires intravenous hydration |
| < 3 years | | Irritability | Requires more cuddling and is less playful than usual | More difficult to settle | Unable to console |
| < 3 years | | Sleepiness | Shows an increased drowsiness | Sleeps through feeds / meals | Sleeps most of the time and it is hard to arouse him / her |
| >= 3 years | | Nausea | No interference with daily activity | Interferes with daily activity | Prevents daily activity |
| | | Fatigue | No interference with daily activity | Interferes with daily activity | Prevents daily activity |
| | | Myalgia | No interference with daily activity | Interferes with daily activity | Prevents daily activity |

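### SAP Table 3 has no grade for 1–10 mm local reactions, so read directly they count as absent, and it regrades fever; SAP section 16 declares neither change

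*SAP*

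**What the plan says.** **Protocol.** Section 8.1.1.1 opens the primary safety endpoints with "Percentages of subjects with solicited local and systemic AEs". Section 8.4.2.1.2 says that erythema, induration and ecchymosis "will be summarized according to categories: 1 to 10 mm, 11 to 25 mm, 26 to 50 mm, >50 mm". It adds "Each solicited local and systemic AE will also be further summarized as" none versus any. In section 8.3.3, an induration of 0 mm is the example of none. Under section 7.1.1, the parent who sees a measurable reaction "should use the ruler provided by the site" and records the size in mm. Fever is "categorized as mild (38.0-38.4°C), moderate (38.5-38.9°C), severe (39.0-40.0°C), and potentially life threatening", the last of these from 40.0 °C upward.

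**SAP.** In section 13.2, Table 3 places three grades under an Any Event heading. The erythema row reads "Erythema | 11-25 mm | 26-50 mm | >50 mm", and ecchymosis and induration have the same cut points. The fever row reads "Fever | 38.0 - 38.9 °C | 39 – 39.9 °C | ≥40.0 °C". The note under the table derives the size grades from the mm values and states that "presence of an event on a day is defined as mild, moderate or severe; absence is defined as none". Table 2 in section 6.3 removes only negative or very large sizes. Section 16 gives changes to the planned analysis as not applicable.

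**The concern.** A reading of 1–10 mm is valid data and a reaction under the protocol, but it has no grade in the SAP. Because the SAP ties presence to having a grade, a programmer who follows Table 3 and its note would code it as absent. The percentage with any erythema, induration or ecchymosis could then only fall or stay the same relative to the protocol's definition. Number of days, daily reports and first onset may move too, since the note defines presence day by day. The combined *any local* and *any solicited* rates change only for children with no other qualifying event.

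For fever the threshold for any event is the same in both documents. The severity labels differ, including *severe* in the SAP's table of any and severe events.

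The same diary data would therefore give different figures under the two documents. Section 16 would lead a reader to believe that nothing had changed.

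**Working it through.** The plan states no figure for this point, so there is none to reproduce. The check sets the two rules side by side and then sizes the difference.

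**1. Size of a local reaction**

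| Largest reading | Protocol 8.4.2.1.2 | SAP Table 3 and note |
|---|---|---|
| 0 mm | none (example in 8.3.3) | no grade, absent |
| 1, 5, 10 mm | 1–10 mm band, any | no grade; absent if read directly |
| 11, 25 mm | 11–25 mm band | mild |
| 26, 50 mm | 26–50 mm band | moderate |
| 51 mm | >50 mm band | severe |

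From 11 mm upward the cut points agree. Only the 1–10 mm band is lost.

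**2. Fever**

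| Temperature | Protocol | SAP |
|---|---|---|
| 38.0–38.4 °C | mild | mild |
| 38.5–38.9 °C | moderate | mild |
| 39.0–39.9 °C | severe | moderate |
| 40.0 °C | severe and potentially life threatening (overlap) | severe |
| above 40.0 °C | potentially life threatening | severe |

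In 0.1 °C steps from 38.0 to 41.9 °C there are 40 values. The label changes for 5 (38.5–38.9) + 10 (39.0–39.9) + 19 (40.1–41.9) = 34 of them. Any fever starts at 38.0 °C in both documents, so its change is 0.

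**3. Effect per child.** Protocol Table 6.1 plans about 70 children per arm and 35 per arm and age cohort. Each child whose largest reading is 1–10 mm lowers *any* for that reaction by:

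- 1/70 = 1.4 percentage points per arm
- 1/35 = 2.9 percentage points per arm and age cohort

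Each child peaking at 39.0–39.9 °C lowers severe fever by the same amounts.

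**4. Assumed range per arm.** Let p be the protocol *any* rate and s the share of those children whose largest reading is 1–10 mm. The number recoded is 70 × p × s, and the SAP rate is p × (1 − s).

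- p = 20%, s = 10%: 70 × 0.20 × 0.10 = 1.4 children; 20% becomes 18%, a fall of 2 points.
- p = 40%, s = 50%: 70 × 0.40 × 0.50 = 14 children; 40% becomes 20%, a fall of 20 points.

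These values of p and s are assumptions; neither document gives reaction rates.

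**5. Registry posting.** SAP 13.3 lists events reported by more than 5% of subjects. If the rule is applied to all 420, then 0.05 × 420 = 21, so at least 22 children are needed. With assumed counts of 28 at 1 mm or more (28/420 = 6.7%) and 7 recoded, 21/420 = 5.0% remains and the reaction drops off the list.

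**The case against.** The strongest reply is that the SAP never says a 1–10 mm reading is none. The note pairs presence with a grade and absence with none, and a 5 mm reading fits neither. The protocol's only example of none is 0 mm. The overall summary in SAP 13.2 reserves *no solicited AE* for a diary with No on every day. On this reading the band is undefined, not absent. That is a fair limit, and the recoding is an inference from Table 3 and its note. But the Any Event heading over grades that start at 11 mm supports the inference, and the alternative leaves a primary endpoint without a rule for valid data.

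Other points stand in part:

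- **Other summaries.** The SAP counts days regardless of severity and defines onset as the first occurrence, without referring back to Table 3. Those summaries may change, but it is not certain.
- **Table shells.** SAP section 17 defers them, so the list of nine summaries does not prove that the band will be left out. Nothing in the SAP puts it in either.
- **Fever.** The 0.5 °C maximum-temperature table still allows counts at 39.0 °C or more, and it separates 38.0–38.4 from 38.5–38.9 °C. Only labels and the severity display change. The protocol's bands overlap at 40.0 °C and needed some repair.
- **Numbers.** The range and the posting example rest on chosen inputs, and SAP 13.3 does not say whether the 5% is pooled or per group. Denominators will also shrink where children have no valid data.
- **Consequence.** One rule applies to all six arms, and the study tests no hypothesis and has no safety success criterion. The endpoint is still a percentage reported by arm and age cohort, and that percentage depends on the rule.

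**Conclusion.** The concern holds. As written, the SAP either counts 1–10 mm erythema, induration and ecchymosis as absent or leaves them unclassified, whereas the protocol counts them as reactions and gives them their own band. It also relabels most febrile temperatures. Neither change is declared.

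On the direct reading the loss in *any* is 1.4 points per affected child per arm and 2.9 points per arm and age cohort, using planned cell sizes. The total is unknown; 2 to 20 points per arm follows only if 20–40% of children react and 10–50% of those peak at 1–10 mm. The >50 mm category and the rate of any fever are unaffected. The mismatch between the documents is certain; the size of its effect is not. It should be fixed before unblinding.

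**What to change.** Amend SAP 13.2 before unblinding:

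1. For erythema, induration and ecchymosis, define *any* as a plausible measurement of 1 mm or more. Apply that rule in the overall summary, number of days, daily reports and first onset. Tabulate none, 1–10, 11–25, 26–50 and >50 mm.
2. Reconcile the fever reporting categories with protocol 8.4.2.1.2, so that 40.0 °C falls in one category only.
3. If the Table 3 scale is also wanted, present it as a second display.
4. Record any intended departure from the protocol, with its reason, in SAP section 16.

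The cost is SAP wording and one re-derivation. The mm and °C values are already collected, so neither data collection nor study conduct changes.
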